2.2 Secondary Goals

2.21 To evaluate safety of pembrolizumab in this patient population.

2.22 To evaluate response rates of pembrolizumab in this patient population.

2.23 To determine the progression free survival, duration of response, time to response and overall survival of pembrolizumab in this patient population .

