11.2 Evaluation of Measurable Disease

11.21 Evaluation of primary cutaneous lesion

mSWAT is calculated using body surface area (BSA) of each MF lesion (palm plus fingers of the patient $\approx 1\%$ BSA) in each of 12 areas of the body, multiplying the sum of the BSA of each lesion type by a weighting factor (patch=1, plaque=2, and tumor =4) and generating a sum of the subtotals of each lesion subtype.

11.211 Measurement of effect

- Overall cutaneous response rate (ORR) = proportion of patients with a 50% or greater reduction of baseline mSWAT score
- Complete cutaneous response rate (CR) = proportion of patients with a 100% reduction of baseline mSWAT score
- Cutaneous 90 response rate (CR90) = proportion of patients with a 90% or greater reduction of baseline mSWAT score without the development of new tumors
- Cutaneous partial response rate (PR) = proportion of patients with a 50-90% baseline reduction of mSWAT score without the development of new tumors
- Progressive cutaneous disease (PD) = greater than 25% increase in baseline mSWAT or the development of new tumors. However, if in the judgement of the investigator, the increase in mSWAT is the result of inflammation due to treatment and/or the unmasking of subclinical skin involvement, this increase in mSWAT shall not be considered evidence of progressive cutaneous disease and the patient shall otherwise be classified as stable cutaneous disease (SD).
- Stable cutaneous disease (SD) = <25% increase to <50% reduction in baseline mSWAT without the development of new tumors ; or patients with a greater than 25% increase baseline mSWAT due to

the result of inflammation due to treatment and/or the unmasking of subclinical skin involvement.

- Relapsed cutaneous disease = Any disease recurrence in those with complete response

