16.0 Statistical Considerations and Methodology

16.1 Overview

This is a phase II study designed to assess the overall cutaneous response rate at cycle 9 in MF patients treated with pembrolizumab. It is a single one-stage design with an interim analysis based on the Simon optimal design with 85% power and 10% Type I error.

NOTE: As per Amendment 4, accrual will cease after the enrollment of 10 patients due to sponsor decision on funding. Thus, the study power and type I error will not be appropriate for the analysis, as the study will not be able to go to full accrual. The study will be analyzed at the pre-defined interim step.

16.11 Endpoint:

The primary endpoint is overall cutaneous response (cutaneous complete response (CR), cutaneous 90 response (CR90) or cutaneous partial response (PR)) as defined using the mSWAT score as stated in section 11.0. Throughout Section 16.0, CR, CR90 or PR will be considered synonymous with “success”, unless specified otherwise. All patients meeting the eligibility criteria who have signed a consent form and have begun treatment will be evaluable for response.

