Duration of response is defined for all evaluable patients who have achieved a CR, CR90 or PR as the date at which the patient's objective status is first noted to be a CR, CR90 or PR to the earliest date relapse is documented. The distribution of duration of complete response will be estimated using the method of Kaplan-Meier.

Time to response is defined as the time from registration to CR, CR90 or PR. The distribution of survival time will be estimated using the method of Kaplan-Meier (Kaplan and Meier 1958).

Overall survival time is defined as the time from registration to death due to any cause. Patients are censored if they are alive at the time of analysis. The distribution of survival time will be estimated using the method of Kaplan-Meier (Kaplan and Meier 1958). In addition, the overall survival rate at 2 years after registration will be reported.

Additional Analyses: All endpoints may be analysed using patient characteristics to explore possible associations of demographics with the endpoints. Possible characteristics include clinical stage, gender and prior treatments.

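### Duration of response is defined for all responders (CR, CR90 and PR), but Section 16.42 specifies the Kaplan-Meier analysis for complete responders only

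*Combined protocol and SAP*

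**What the plan says.** Goal 2.23 in Section 2.2 sets the aim: "To determine the progression free survival, duration of response, time to response and overall survival of pembrolizumab in this patient population". It is not limited to any response category.

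Section 16.42 defines the endpoint to match: "Duration of response is defined for all evaluable patients who have achieved a CR, CR90 or PR", counted from the first date of that status "to the earliest date relapse is documented". The sentence after it gives the estimate: "The distribution of duration of complete response will be estimated using the method of Kaplan-Meier".

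Section 11.211 keeps the categories apart. Its entry for CR reads "Complete cutaneous response rate (CR) = proportion of patients with a 100% reduction of baseline mSWAT score", while CR90 and PR have lower thresholds of their own. The same list defines the end event: "Relapsed cutaneous disease = Any disease recurrence in those with complete response". Section 16.11 pools the three categories for the primary endpoint, stating that "CR, CR90 or PR will be considered synonymous with" success.

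No other section specifies an analysis of duration in CR90 or PR patients. Section 16.31 records that accrual ends at 10 patients under Amendment 4.

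**The concern.** Two adjacent sentences set different populations for one secondary endpoint. An analyst who follows the definition puts every responder in the curve. An analyst who follows the estimation sentence leaves out every CR90 and PR patient. Each could cite the plan, and with about 10 patients that choice should not be made after the data are seen.

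The two populations also follow different paths. Sections 13.3 and 13.5 take patients off treatment at CR. Sections 13.1 and 13.6 keep CR90 and PR patients on treatment, up to a maximum of 24 months. A CR-only curve would therefore describe the deepest responders, who have stopped drug, yet it would be reported as duration of response. It would not describe the patients counted as successes in the primary endpoint. Section 16.34 names duration of response among the considerations in any decision to terminate the study, so the result is meant to be used.

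**Working it through.** **1. Who is covered, place by place**

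| Place | Patients covered |
|---|---|
| Goal 2.23 | Responders, no restriction |
| 16.11, success | CR, CR90, PR |
| 16.42, definition of duration | CR, CR90, PR |
| 16.42, Kaplan-Meier sentence | Complete response only |
| 11.211, relapse (the end event) | Complete response only |

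Because 11.211 gives CR its own threshold (100% reduction), the term cannot be read as covering CR90 and PR.

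**2. The plan's nearest figure.** The documents give no figure for the number of complete responders. The closest is the interim stopping row in Section 16.33, which is the chance of zero or one success in 10:

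P(0 or 1) = (1 − p)^10 + 10 × p × (1 − p)^9

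At p = 0.15: 0.85^10 + 10 × 0.15 × 0.85^9 = 0.197 + 0.347 = 0.544, as stated. At p = 0.20, 0.25, 0.30 and 0.35 the formula gives 0.376, 0.244, 0.149 and 0.086, also as stated. This row counts all successes, so it confirms the method but says nothing about CRs.

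**3. Size of the CR-only curve.** The same formula applies with an assumed CR rate q in 10 patients:

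| Assumed q | Expected CRs (10 × q) | P(no CR) | P(0 or 1 CR) | P(2 or more) |
|---|---|---|---|---|
| 2% | 0.2 | 0.817 | 0.984 | 0.016 |
| 5% | 0.5 | 0.599 | 0.914 | 0.086 |
| 10% | 1.0 | 0.349 | 0.736 | 0.264 |
| 15% | 1.5 | 0.197 | 0.544 | 0.456 |
| 20% | 2.0 | 0.107 | 0.376 | 0.624 |
| 35% | 3.5 | 0.013 | 0.086 | 0.914 |

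The 35% row is the case in which the response rate is at the design target and every responder is a CR.

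The assumption can also be put as a share of responders. If half of responders were CR, then q = 0.15 × 0.5 = 0.075 at the null rate (0.75 expected, P(0 or 1) = 0.830) and q = 0.35 × 0.5 = 0.175 at the target rate (1.75 expected, P(0 or 1) = 0.456).

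**4. Size of the all-responder curve.** At the 15% response rate, 10 × 0.15 = 1.5 patients are expected and P(0 or 1) = 0.544. At 35%, 10 × 0.35 = 3.5 are expected and P(0 or 1) = 0.086.

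**5. Can the wider curve be computed from the plan?** Not yet. Duration ends at relapse, and 11.211 defines relapse only after complete response. A CR90 or PR patient has no defined end event, so changing the population alone is not enough.

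**The case against.** The strongest reply is that this is a slip of wording. Section 16.21 words the null hypothesis as a complete response rate although the endpoint is CR, CR90 or PR. In 16.42 the time-to-response paragraph goes on to speak of survival time. The opening of 16.42 keeps in the secondary analyses patients who did not reach a complete or partial response. An analyst would probably apply the stated definition. This is plausible, but it does not settle the matter: the end event in 11.211 exists only for complete responders, which fits the literal CR-only reading.

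A second reply is that the gain is small, and this stands. At a 15% response rate the all-responder curve has the same 0.544 chance of resting on zero or one patient as a CR-only curve has at a 15% CR rate. Kaplan-Meier will be imprecise either way.

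Two stronger readings are tempting and are not supported:

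- A reader might infer that the CR-only curve will rest on zero or one patient. That needs a CR rate that the documents do not give. At 15% the chance of two or more CRs is already 0.456, and at 20% it is 0.624.
- A reader might infer that the CR-only curve overstates durability. Complete responders stop drug, and any recurrence counts as relapse for them; both could shorten their measured duration. The direction is not known.

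**Conclusion.** The inconsistency is real and holds whatever the CR rate. Read literally, Section 16.42 defines an endpoint for all responders and then analyses a subset, so it does not answer goal 2.23. The curve would misdescribe duration of response, with no established direction.

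How few patients it would hold depends on an assumed CR rate. Across 2% to 35%, the chance of zero or one CR in 10 patients runs from 0.98 down to 0.09. The fair statement is that the curve could rest on very few patients, possibly none or one. These figures assume 10 evaluable patients with independent outcomes and a common rate.

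This is a secondary endpoint, and correcting it will not make the estimate precise. It should be corrected because the edit is nearly free and removes a choice that would otherwise be open when the data are read.

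**What to change.** Three changes in Section 16.42, made together:

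1. Reword the estimation sentence so that Kaplan-Meier is applied to duration of response in all patients with CR, CR90 or PR.
2. State an end event that applies to CR90 and PR patients. One option is documented progression under the existing PD criteria in Section 11, alongside relapse after CR. Cutaneous PD in 11.211 is measured against baseline mSWAT, so the team should confirm that this is the loss of response it wants to time.
3. List each responder's duration and best response category, with CR patients marked as off drug. With so few patients this listing will carry most of the information.

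The cost is a few sentences and a short listing. No new data are needed. The curve will still be imprecise.

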13.2 Progressive disease (PD)

Patients who develop PD (non-responders) during cycle 1 will exit the study (no follow-up). Patients who develop PD subsequent while receiving therapy will complete the End of Treatment visit at the time of PD and repeat staging per protocol, then proceed to survival follow-up (Section 4.2).

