13.3 Off protocol treatment

Patients who do not develop PD during cycle 1 and go off protocol treatment for reasons other than PD within any cycle will proceed to survival follow-up. Note: This does not apply to patients receiving alternative therapy. Patients who go off treatment for alternative therapy will exit the study (no follow-up).

Patients who achieve CR at any time will proceed to survival follow-up.

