16.4 Analysis Plan

16.41 Primary Outcome Analysis: The mSWAT score at baseline and cycle 9 will be used for change in baseline calculations. All calculated values will use the last-observation-carried forward for any participants who withdraw, are lost to follow up, or exit the study per protocol. The proportion of successes will be estimated by the number of successes divided by the total number of evaluable patients will be analysed using Mann-Whitney U for nonparametric data and the student t-test. Confidence intervals for the true success proportion will be calculated according to the approach of Duffy and Santner (Duffy D 1987).

16.42 Secondary Outcome Analysis: These analyses will include all patients meeting the eligibility criteria who have signed a consent form and have begun treatment, including patients who fail to achieve a complete or partial response.

Adverse Events: All eligible patients that have initiated treatment will be considered evaluable for assessing adverse event rate(s). The maximum grade for each type of adverse event will be recorded for each patient, and frequency tables will be reviewed to determine patterns. Additionally, the relationship of the adverse event(s) to the study treatment will be taken into consideration.

Response Rates:

Changes in mSWAT scores from baseline will be evaluated at cycle 9. Summary statistics will be calculated.

Patients will be assigned response based on the mSWAT criteria in section 11.0. Proportions of patients will be calculated and described using summary statistics. Proportions of interest are patients having CR, CR90 and PR; patients having stable subcutaneous disease; patients having progressive cutaneous disease; and patients having an overall systemic response rate.

Progression free survival time is defined for all evaluable patients as the time from registration to relapse or death due to any cause. Patients are censored if they have not achieved a progression at the time of analysis. The distribution of progression-free survival will be estimated using the method of Kaplan-Meier. In addition, the progression-free survival rate at 5 years after registration will be reported.

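### Time to response is assigned Kaplan-Meier with no rule for patients who progress, die or exit before responding; under usual censoring the curve can overstate the chance of responding

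*Combined protocol and SAP*

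**What the plan says.** Section 16.42 opens by defining the set for the secondary analyses as all eligible, consented patients who began treatment, "including patients who fail to achieve a complete or partial response". For this endpoint it then states "Time to response is defined as the time from registration to CR, CR90 or PR", followed directly by "The distribution of survival time will be estimated using the method of Kaplan-Meier (Kaplan and Meier 1958". The same estimator sentence appears again in the overall survival paragraph.

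Two neighbouring endpoints have a censoring rule. For progression-free survival: "Patients are censored if they have not achieved a progression at the time of analysis". For overall survival: "Patients are censored if they are alive at the time of analysis". Time to response has none, and Section 16.42 mentions no competing-risk method.

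Other sections show what ends observation of response:

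- Section 13.2: "Patients who develop PD (non-responders) during cycle 1 will exit the study (no follow-up". Patients who progress later have an End of Treatment visit with repeat staging and then go to survival follow-up.
- Section 13.3: "Patients who go off treatment for alternative therapy will exit the study (no follow-up". Patients who stop for other reasons go to survival follow-up.
- Section 11.41: mSWAT is recorded at baseline, at the end of each cycle, and at the 30- and 90-day clinical follow-up visits. Section 4.2 lists no mSWAT during survival follow-up.

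**The concern.** A patient who has progressed or died cannot later be recorded as a responder. Kaplan-Meier treats a censored patient as someone who would have gone on to respond at the same rate as those still under observation. Applied to progression and death, it estimates how quickly patients would respond if nobody progressed or died, which is not the proportion of treated patients who respond by a given time.

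Time to response is a named secondary goal (Section 2.23). Accrual stops at 10 patients (Section 16.1), so each early exit changes the risk set noticeably. A published curve could end well above the fraction of the 10 patients who ever responded. Because the handling rule is missing, two analysts following the text could also draw different curves from the same data.

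**Working it through.** **Plan's own figure.** The plan states no figure for time to response, so there is none to reproduce. It also gives no rate of progression, death or exit before response. All event patterns below are assumptions.

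**Direction.** At each time let n be the number at risk, d1 the responses and d2 the competing events.

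- 1-KM with competing events censored: S is multiplied by (1 − d1/n), and each step adds S × d1/n.
- Cumulative incidence (Aalen-Johansen): O is multiplied by (1 − (d1 + d2)/n), and each step adds O × d1/n.

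O carries extra reductions from d2, so O ≤ S at every time. Hence 1-KM is never below the cumulative incidence, and it is strictly above it once a response occurs after a censored competing event.

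**Ten-patient illustration.** Assume 4 responses (R), 4 progressions (P) and 2 patients stable to the end, with distinct event times.

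| Order of events | At risk at each response | 1-KM |
|---|---|---|
| RRRRPPPP | 10, 9, 8, 7 | 1 − (9/10)(8/9)(7/8)(6/7) = 0.40 |
| RPRPRPRP | 10, 8, 6, 4 | 1 − (9/10)(7/8)(5/6)(3/4) = 0.51 |
| PRPRPRPR | 9, 7, 5, 3 | 1 − (8/9)(6/7)(4/5)(2/3) = 0.59 |
| PPPPRRRR | 6, 5, 4, 3 | 1 − (5/6)(4/5)(3/4)(2/3) = 0.67 |

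Over all 70 orderings, 1-KM runs from 0.40 to 0.67 with mean 0.55. The cumulative incidence is 4/10 = 0.40 in every one. If the four progressed patients are instead kept at risk to the end of follow-up, the at-risk numbers are 10, 9, 8, 7 and Kaplan-Meier also gives 0.40.

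**Constant-hazard illustration over 24 months.** Let R be the true probability of response and C the assumed probability of progression or death before response. With L = −ln(1 − R − C), 1-KM = 1 − exp(−L × R/(R + C)). Section 16.21 supplies R = 0.15 and 0.35; C is assumed. For R = 0.35 and C = 0.30, L = −ln(0.35) = 1.050, and 1.050 × 0.35/0.65 = 0.565, so 1-KM = 1 − exp(−0.565) = 0.432.

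| True response | C = 0.20 | C = 0.30 | C = 0.50 |
|---|---|---|---|
| 0.15 | 0.169 | 0.181 | 0.215 |
| 0.35 | 0.398 | 0.432 | 0.542 |

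The excess is about 2 to 19 percentage points. For scale, the design separates 15% from 35%, a gap of 20 points.

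**Simulated 10-patient trials.** With 10,000 trials per scenario on a 35-cycle grid, mean 1-KM against mean cumulative incidence was 0.182 against 0.152 (R = 0.15, C = 0.30), 0.430 against 0.351 (0.35, 0.30) and 0.530 against 0.350 (0.35, 0.50). Over the five scenarios run, 1-KM was strictly higher in 62% to 95% of trials and never lower.

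**The case against.** The strongest reply is that the plan never says progressed or deceased patients are censored for this endpoint. That is correct. A reader might infer that the reported curve will overstate response, but the documents do not support so firm a statement. The excess is zero if non-responders stay at risk to the end of follow-up, or if every response comes before every competing event. What remains is that the plan allows both readings, and the usual convention is the one that produces the excess.

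It can also be said that the estimator sentence names survival time and repeats the overall survival text, so it may be carried over by mistake. That is plausible, but it leaves time to response with no correctly specified estimator, which is a reason to amend the sentence.

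A reader might also compare the curve with the primary response proportion and take any difference as bias. That comparison is unsound. The primary proportion is assessed at cycle 9 (Sections 16.1 and 16.41), while responses can occur during up to 24 months of treatment, so a correct cumulative incidence curve could also end above it. The fair comparator is the proportion ever responding.

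Finally, the harm is bounded. Section 16.41 estimates response as successes over evaluable patients, and the interim rule in Section 16.22 uses a count. Neither reads from this curve. That stands in full.

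**Conclusion.** The point holds in conditional form. Kaplan-Meier is the only estimator named, non-responders are in the set, progression, death and exit end response assessment, and no handling rule is given. If these patients are censored at the event or at their last mSWAT, 1-KM is at least the cumulative incidence and usually above it.

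The size depends on how many competing events occur and when, which the documents do not say. The 0.40 to 0.67 range and the 2 to 19 point excess are illustrations under assumed patterns, not predictions for this trial. The consequence is confined to one secondary endpoint in a 10-patient study. This is a cheap improvement.

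**What to change.** In Section 16.42, take one of two routes:

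1. Estimate time to response by cumulative incidence (Aalen-Johansen), with progression and death before response as competing events. State separately how other exits without response are handled (alternative therapy, toxicity, withdrawal). These need not all be competing events, since stopping treatment for such a reason does not by itself rule out response, but the choice should be written down.
2. Report the median and range of time to response among responders only, labelled as such. With 10 patients this may be enough.

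Under either route, make the estimator sentence refer to time to response instead of survival time.

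The cost is a few lines of wording and a small amount of extra analysis. No new data, visits or patients are needed. The reported curve may be lower than a Kaplan-Meier curve with censoring would have been.

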6.6 Treatment start

Treatment cannot begin prior to registration and must begin ≤ 28 days after registration.

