13.0 Treatment/Follow-up Decision at Evaluation of Patient

Reason Off Treatment (from the Off Treatment Form)	Go to CFU, SFU, or end folder rollout
1 = Treatment (Intervention) Completed Per Protocol Criteria	CFU
2 = Patient Withdrawal/Refusal After Beginning Protocol Therapy (Intervention)	SFU
3 = Adverse Events/Side Effects/Complications	SFU
4 = Disease Progression, Relapse During Active Treatment (Intervention)	SFU
5 = Alternative Therapy	No follow-up
6 = Patient Off-Treatment (Intervention) For Other Complicating Disease	SFU
7 = Death On Study	No follow-up
8 = Other	SFU
10 = Disease Progression Before Active Treatment (Intervention)	No follow-up
24 = Patient Withdrawal/Refusal Prior To Beginning Protocol Therapy (Intervention)	No follow-up

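### Time to response, PFS and OS are timed from registration but analysed only in treated patients, so each time may carry up to 28 untreated days

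*Combined protocol and SAP*

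**What the plan says.** Goal 2.23 is "To determine the progression free survival, duration of response, time to response and overall survival of pembrolizumab in this patient population". Section 16.42 then sets the clocks:

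- Time to response: "Time to response is defined as the time from registration to CR, CR90 or PR".
- PFS: "Progression free survival time is defined for all evaluable patients as the time from registration to relapse or death due to any cause".
- OS: "Overall survival time is defined as the time from registration to death due to any cause".

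The population for all of these is fixed at the head of 16.42: "These analyses will include all patients meeting the eligibility criteria who have signed a consent form and have begun treatment". Section 16.11 defines evaluability in the same way: patients who meet eligibility, consent and "have begun treatment will be evaluable for response".

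The interval between the two events is governed by Section 6.6: "Treatment cannot begin prior to registration and must begin ≤ 28 days after registration".

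Patients lost in that interval are handled elsewhere. Section 13.0 has off-treatment codes for progression before treatment (code 10) and withdrawal before treatment (code 24), both without follow-up. Section 13.9 classes anyone removed before dosing as a cancel and asks for no data beyond the on-study material and the notification form. Footnote 7 to the test schedule in Section 4.1 records Cycle 1 Day 1, before treatment, as baseline. Section 11.41 places the next mSWAT at the end of cycle 1.

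**The concern.** The clock starts at one event (registration), while entry to the analysis set depends on a later one (first dose). The time between them is counted as follow-up, yet a patient who dies in it never enters the set. This is immortal time. A registration clock is coherent when all registered patients are analysed, and a first-dose clock is coherent for treated patients. The plan combines the first clock with the second population.

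The two consequences run in opposite directions. PFS and OS look slightly longer, because waiting time is credited as event-free time and early failures drop out. Time to response looks slower, because days without the drug are added to an endpoint that is meant to describe pembrolizumab. The amount added depends on scheduling and can differ between patients.

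**Working it through.** The plan states no figure that depends on the time origin, so there is nothing to reproduce. The check is a comparison of the definitions, then a sizing.

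**Inputs from the documents.** Lag L from registration to first dose: 0 to 28 days (6.6). Cycle length: 21 days (4.1). First post-baseline mSWAT: end of cycle 1 (11.41), about day 21 after first dose, with a visit window of 3 days either way (4.1). Landmarks: 2-year OS and 5-year PFS, both from registration (16.42). Accrual: 10 patients (16.31, Amendment 4).

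**Assumptions, not in the documents.** Exponential times from first dose; 2-year survival of 80%, 60% or 40%; median PFS of 12 or 6 months. The worst case has every patient waiting 28 days.

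**Which events can fall in the gap?**

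- Death: none, by definition of the set. A treated patient was alive at first dose.
- Response: none can be recorded. No mSWAT is scheduled between the baseline value and the end of cycle 1.
- Progression: excluded in practice, because such a patient can be taken off under code 10. No sentence expressly bars dosing after progression in the gap.

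**Time to response.** Recorded time = time from first dose + L.

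| Response first recorded at | Days from first dose | Days from registration | Added at L = 28 |
|---|---|---|---|
| End of cycle 1 | 21 | 21 to 49 | 28/21 = 133% |
| End of cycle 3 | 63 | 63 to 91 | 28/63 = 44% |
| End of cycle 9 (week 27) | 189 | 189 to 217 | 28/189 = 15% |

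In the first row, up to 28/49 = 57% of the recorded time is untreated.

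**2-year OS.** Let s be 2-year survival from first dose and λ = −ln(s)/730.5 per day. For treated patients timed from registration, the 2-year value is exp(−λ(730.5 − L)).

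| s from first dose | L = 14 | L = 28 | Rise at L = 28 |
|---|---|---|---|
| 0.800 | 0.803 | 0.807 | 0.7 points |
| 0.600 | 0.606 | 0.612 | 1.2 points |
| 0.400 | 0.407 | 0.414 | 1.4 points |

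**5-year PFS.** With a 12-month median, the value from first dose is 0.5^5 = 3.1%. With L = 28 it is 0.5^((1826.25 − 28)/365.25) = 0.5^4.923 = 3.3%. With a 6-month median it goes from 0.10% to 0.11%.

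**Medians.** If every lag were 28 days (28/30.44 = 0.92 months), a first-dose median of 3, 6, 12 or 24 months would be overstated by 31%, 15%, 8% or 4%.

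**The case against.** The best defence is that registration is a convention used throughout the plan. Survival follow-up ends 2.5 years after registration (4.2), and the primary endpoint completion date is counted from the last patient registered (16.5). Goal 2.23 names no time origin, and with a single arm there is no treatment contrast to distort. This explains the choice but does not repair it. The convention works when all registered patients are analysed, and 16.42 does not do that. No section left-truncates at first dose or otherwise removes the gap.

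The objections on size are sound. A reader might infer that every recorded time contains an untreated stretch. The documents do not support that: 6.6 sets only a maximum, same-day dosing is allowed, and no typical delay is given. A reader might also infer that the gap is event-free by construction for all three endpoints. That holds for death and for recorded response. For progression it rests on how code 10 is used. The 133% figure pairs the longest lag with the earliest possible response, so it is an extreme and not an expected bias.

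Nor is it shown that unequal lags add material noise. mSWAT is taken once per 21-day cycle, so a lag of 0 to 28 days is at most a little over one assessment interval.

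**Conclusion.** The mismatch between time origin and population is real and is in the current text. It is a minor point, worth correcting because correction is cheap.

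It matters most for time to response, where up to 28 days of waiting is added to an endpoint whose first scheduled assessment is about 21 days after dosing. For PFS and OS the direction is upward and the size small at the plan's own landmarks: about 0.7 to 1.4 points for 2-year OS, and 0.2 points or less for 5-year PFS. Those figures rest on exponential times, the assumed rates above and a full 28-day wait for everyone; shorter waits give less. With 10 patients, one patient is 10 percentage points, so sampling error dwarfs the shift. The documents do not support a claim that PFS or OS would be seriously misleading.

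Duration of response is unaffected, because its clock starts at the first response.

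**What to change.** In 16.42, define time to response, PFS and OS from the date of first pembrolizumab dose (Cycle 1 Day 1), and take the landmark rates from the same origin. Every patient in the set has that date, and footnote 7 of Section 4.1 already treats Cycle 1 Day 1 as baseline. Origin, population and baseline then agree.

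The cost is wording only, with no new visits. The 2-year OS landmark stays within follow-up: at most 730.5 + 28 = 758.5 days from registration, against 2.5 years (about 913 days) in Section 4.2. The 5-year PFS landmark lies beyond that follow-up under either origin; this is a separate matter that the change neither causes nor solves. The downsides are that PFS and OS become slightly shorter and that the clock departs from a registration-based convention.

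A companion analysis over all registered patients should not be promised as a free addition. Outcomes are not collected for cancelled patients or for those off under codes 10 and 24. Such a line should be left out or limited to the data available.
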